5.2 Frequency and rate of events

The frequency of medical events is defined as the total number of each individual event. The frequency will be described by absolute number of each individual medical event and percentage of each individual medical event of total number of captured medical events during the observation period.

The rate of medical events is defined as the number of all captured events divided by the total person-time following MenACWY-CRM doses administered during the study period. The rate and Poisson 95% confidence interval of the rate of medical events will be calculated and presented as number per 1000 person-years.

If the number of medical events allows, captured medical events will be stratified by dose and by the status of the diagnosis as first occurrence or recurrence. Person-time for each dose will begin at the vaccination and end at 6 months following vaccination, disenrollment, death, the end of data collection, or receipt of an additional dose of MenACWY-CRM, whichever comes first.

Frequency and rate of events will be characterized two ways: by encounter (hospitalization only, ED only, or both ED and hospitalization) and by diagnosis (see Appendix A, Table Shell 5 for details). For the analysis by encounter, the encounter date will be used to determine the timing of the encounter relative to the timing of vaccine dose. For the analysis by diagnosis, the first diagnosis date for each diagnosis in any care setting will be used to determine the timing of the diagnosis relative to the timing of vaccine dose. The analysis by diagnosis will be stratified by setting of diagnosis and recurrence when the number of events in each stratum is ≥ 5 . The setting of diagnosis reflects whether the diagnosis was captured by automated search in the inpatient setting, ED setting, or both. If possible, diagnoses will be grouped by category, and the frequency and rate of diagnoses will be presented by category.

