3.2 Sample Size and Power Considerations

As the study is descriptive in nature, there is no hypothesis testing and therefore no requirement for a given sample size or power. The sample size will be determined by the total number of children aged 2-23 months vaccinated in KPSC during a three-year period.

Approximately 245,000 infants and toddlers aged 2-23 months were enrolled in the KPSC health plan in the period from 2011 to 2013. Among this population, there were around 60 children aged 2-23 months old with high risk medical conditions. It is estimated that the number of infants with high risk conditions would likely fall between 60-100 in the study period.

The following table provides the width of the confidence intervals for the incidence rate estimates for different sample sizes and observed event rates. It assumes that each individual recipient will provide, on average, one person-year of follow-up among all doses.

Table: Expected confidence intervals by event rate and study sample size.

Event rate per 100 person-years	Number of vaccinated subjects		
	N=50	N=100	N=150
0.1	0.0-7.6	0.0-3.9	0.0-2.7
1.0	0.0-9.4	0.0-5.6	0.1-4.3
10	3.3-23.3	4.8-18.4	5.6-16.5
100	74.2-131.8	81.4-121.6	84.6-117.3

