5.2 Frequency and rate of events

The frequency of medical events is defined as the total number of each individual event. The frequency will be described by absolute number of each individual medical event and percentage of each individual medical event out of the total number of captured medical events during the observation period and included for analysis (as per Tables 4a or 4b).

The rate of medical events is defined as the number of all captured events divided by the total person-time following MenACWY-CRM doses administered during the study period. The rate and Poisson 95% confidence interval of the rate of medical events will be calculated and presented as number per 1000 person-years using SAS PROC GENMOD.

If the number of medical events allows, captured medical events will be stratified by dose and by the status of the diagnosis as first occurrence or recurrence. Person-time for each dose will begin at the date of vaccination and end at 6 months following vaccination, disenrollment, death, the end of data collection, or receipt of an additional dose of MenACWY-CRM, whichever comes first.

Frequency and rate of events will be characterized two ways: by encounter (hospitalization only, ED only, or both ED and hospitalization) and by diagnosis (see Appendix A, Table Shell 5 for details). For the analysis by encounter, the encounter date will be used to determine the timing of the encounter relative to the timing of vaccine dose. For the analysis by diagnosis, the first diagnosis date for each diagnosis in any care setting will be used to determine the timing of the diagnosis relative to the timing of vaccine dose. The analysis by diagnosis will be stratified by setting of diagnosis and recurrence when the number of events in each stratum is ≥ 5 . The setting of diagnosis reflects whether the diagnosis was captured by automated search in the inpatient setting, ED setting, or both. If possible, diagnoses will be grouped by category, and the frequency and rate of diagnoses will be presented by category.

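### SAP 5.2 names PROC GENMOD for the Poisson rate intervals without saying which interval; its default log-scale Wald limits do not match the table in 3.2 and are poor at 0-4 events

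*SAP*

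**What the plan says.** SAP v2.0, section 5.2, defines the rate as captured events over person-time and continues: "The rate and Poisson 95% confidence interval of the rate of medical events will be calculated". The same sentence ends "will be calculated and presented as number per 1000 person-years using SAS PROC GENMOD". SAP v1.2 has this sentence without the procedure. Neither version names Wald, likelihood-ratio or exact limits, or says how a row with zero events is handled. The protocol (Statistical Methods) asks only for a 95% confidence interval.

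SAP section 3.2 introduces its precision table with "The following table provides the width of the confidence intervals for the incidence rate estimates for different sample sizes and observed event rates". On follow-up it says: "It assumes that each individual recipient will provide, on average, one person-year of follow-up among all doses". It names no interval method. The table is the same in v1.2 and v2.0. The number of high-risk children "would likely fall between 60-100 in the study period".

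Minimum counts apply to some outputs only. Setting and recurrence strata need at least 5 events (5.2). Other strata need n of at least 5, without saying whether n counts recipients or events (sections 5 and 8). Table 6 needs at least 5 episodes. The Overall columns of Tables 5a and 5b have no minimum.

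**The concern.** Sections 3.2 and 5.2 appear to use different intervals. The table in 3.2 tells the reader what precision to expect. If 5.2 is run at the procedure's default, the reported limits will come from another method, and the two differ most at small counts.

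The study has no comparator and no hypothesis test, so the rates and their intervals are its only inferential output. A row with no events would be printed without an upper limit. A diagnosis seen once or twice would carry a lower limit well above the exact one.

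**Working it through.** **Inputs.** Person-years: one per recipient (SAP 3.2), so 50, 100 and 150 for the table. For illustration I use 80 person-years, the midpoint of 60-100 children at one person-year each. Two-sided 95% limits are assumed; the SAP does not state sidedness. It is also an assumption that GENMOD would be run at its default. I take that default to be the log-scale Wald interval; an intercept-only log-link Poisson model with a person-time offset, fitted at 1-5 events, gave these limits.

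**Formulas**, for x events in T person-years:

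- Exact: lower = chi2(0.025; 2x) / (2T), taken as 0 at x = 0; upper = chi2(0.975; 2x+2) / (2T).
- Log-scale Wald: (x/T) × exp(±1.96/√x), undefined at x = 0.

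**Step 1: reproduce the 3.2 table.** Put x = rate × N/100, allowing fractions. The exact formula gives 22 of the 24 printed limits to one decimal. The other two (3.247 printed as 3.3, 9.348 printed as 9.4) fit double rounding. Log-scale Wald does not fit:

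| Cell (per 100 person-years) | Events | Printed | Exact | Log-Wald |
|---|---|---|---|---|
| Rate 1.0, N=100 | 1 | 0.0-5.6 | 0.03-5.57 | 0.14-7.10 |
| Rate 10, N=50 | 5 | 3.3-23.3 | 3.25-23.34 | 4.16-24.03 |
| Rate 10, N=100 | 10 | 4.8-18.4 | 4.80-18.39 | 5.38-18.59 |

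**Step 2: limits at small counts**, per 1000 person-years with T = 80:

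| Events | Exact | Log-Wald | Lower-limit ratio | Upper-limit ratio |
|---|---|---|---|---|
| 0 | 0-46.1 | none | – | – |
| 1 | 0.3-69.6 | 1.8-88.7 | 5.56 | 1.27 |
| 2 | 3.0-90.3 | 6.3-100.0 | 2.07 | 1.11 |
| 3 | 7.7-109.6 | 12.1-116.3 | 1.56 | 1.06 |
| 4 | 13.6-128.0 | 18.8-133.2 | 1.38 | 1.04 |
| 5 | 20.3-145.9 | 26.0-150.2 | 1.28 | 1.03 |

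The ratios do not depend on T. By 10 events the lower-limit ratio is 1.12, and by 50 it is 1.02. At zero events the exact upper limit is 3.69/T: 61.5 at 60 person-years, 46.1 at 80 and 36.9 at 100.

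**Step 3: coverage given at least one event**, from summed Poisson probabilities:

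| Expected events | Log-Wald | Exact |
|---|---|---|
| 0.5 | 77% | 96% |
| 1 | 97.0% | 97.0% |
| 2 | 93.9% | 98.1% |
| 3 | 96.5% | 98.7% |
| 5 | 96.8% | 98.6% |

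**Step 4: where such cells can be reported.** Table 5a has three fixed rows (hospitalization only, emergency department only, both), any of which can be zero. Table 5b lists observed diagnoses one by one, so its Overall column starts at one event and is likely to hold many rows with 1-4. Dose columns can hold zero-event cells if the n of at least 5 means recipients.

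**The case against.** The strongest reply is that 5.2 names a procedure and not an interval. The poor limits follow from default use, which the SAP does not prescribe. This stands: the documented defect is an unspecified option. A reader might infer that the named procedure cannot give a usable limit, but the text does not go that far. Choosing another option would still need saying, because the answers differ: at zero events the likelihood-ratio upper limit is 1.92/T, against 3.69/T for exact.

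Four other strong readings also fail.

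- *Section 3.2 promises exact limits.* It illustrates precision and names no method. That the limits are exact is inferred from recomputation.
- *The default could not deliver the printed limits of 7.6, 3.9 and 2.7 in the 0.1 row.* Neither could exact limits. Those values come from 0.05, 0.10 and 0.15 events, which no study can observe. At zero events the exact upper limits are 7.38, 3.69 and 2.46 per 100 person-years.
- *Coverage falls to 61% at one expected event and 81% at two.* These figures count every zero-event study as a failure (probabilities 37% and 14%). A Table 5b row exists only when the diagnosis is observed, so Step 3 gives the relevant comparison.
- *For a diagnosis never seen, the upper limit is the whole safety message.* No list of events of interest is specified and Table 5b shows observed diagnoses, so that output is not planned.

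It is also fair to say that the consequence is limited. At one event both intervals say that the rate is very imprecise. The Wald upper limit is the higher of the two, which is cautious for safety. The 5-event rules protect setting and recurrence strata.

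**Conclusion.** The concern holds in a limited form. Section 5.2 leaves the interval unspecified, and the procedure's default disagrees with the method that reproduces 3.2. Under that default a zero-event row has no interval, and limits at 1-4 events differ from exact ones by the factors in Step 2. The coverage loss, given at least one event, lies mainly below one expected event and is slight at two.

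This rests on three assumptions: default log-scale Wald limits would be used; follow-up is near one person-year per child; and the cohort is near the 60-100 high-risk children of 3.2. The first decides whether the problem arises at all. The other two affect only the absolute limits and how often small counts occur. It is a minor to moderate correction, not one that must be made before the study can be reported.

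**What to change.** In SAP 5.2, replace the reference to PROC GENMOD with exact (chi-square) Poisson 95% limits for all rate rows in Tables 5a and 5b. State the zero-event case: lower limit 0, upper limit 3.69 divided by person-years. Using one method for every row avoids having to define which rows are sparse. A few words in 3.2 naming the same method would make the agreement explicit.

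The cost is one sentence and a few lines of SAS. The downside is slightly conservative intervals, as the exact coverage in Step 3 shows. If the sponsor prefers to keep GENMOD, 5.2 should name the interval option and a zero-event rule, and the 3.2 table should be rebuilt with that method.

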5.1 Identification and review of events

Medical events occurring in ED and inpatient settings within 6 months following a MenACWY-CRM vaccination will be searched in the EMR.

Medical events will be characterized two ways: by encounter (hospitalization only, ED only, or both ED and hospitalization) and by diagnosis (see Appendix A, Table Shell 4 for details). The analysis allows for any recurrent events (i.e. different episodes of the same diagnosis) to be counted independently.

For characterization by encounter (Table 4a), all dates used for analysis will be the date of the ED encounter or hospital admission. Encounters will be considered pre-existing if all diagnoses made during the encounter are present in the medical record prior to the first dose of vaccine. Upon chart review by the study physician co-investigator, an encounter will be refuted if it is found to not be a true ED or hospital encounter. Each encounter will be reported as a single event, regardless of the number of diagnoses made during the encounter.

For characterization by diagnosis (Table 4b), all dates used for analysis will be the first date that the diagnosis is recorded in the EMR in any medical setting. A diagnosis will be excluded as pre-existing if the same ICD diagnosis code appears in any medical setting prior to the first dose of MenACWY-CRM vaccination. A diagnosis will be considered refuted if, upon chart review by the study physician co-investigator, there is no evidence of the diagnosis in the medical record. Multiple diagnoses associated with the same episode will be identified, but only the first diagnosis date (in any setting) will be counted in the analysis of each episode. Subsequent diagnoses for the same episode will be marked in Table 4b as “Diagnosis is continuation of an ongoing episode.” An episode will be considered as ended when there is symptom resolution as determined by chart review (e.g., symptoms stated to have resolved or the diagnosis/symptoms have been absent from the medical record before they are mentioned again). In the case of recurrent events, the date used will be the date of the first diagnosis in the medical record following resolution of the prior episode. Recurrent events will be marked in Table 4b as “Diagnosis is a recurrence”. Each diagnosis will be described independently. It is possible that different diagnoses from the same inpatient or ED encounter could have different diagnosis

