Number of recipients experiencing multiple different hospitalization or emergency encounters							
N/A = Not Applicable							

Table 4b: Summary of Diagnosis Identification and Review

Event	Automated Algorithm			Physician Review			Diagnosis is continuation of an ongoing episode (g)	Diagnosis is a recurrence (h)	Total Diagnoses for Analysis (i=a-b-e-f-g)
	Potential diagnoses identified (a)	Excluded diagnoses based on pre-existing condition (b)	Diagnoses remaining from automated algorithm identification (c=a-b)	Diagnoses confirmed (d)	Diagnoses refuted (e)	Confirmed events with diagnosis determined to be prior to index vaccination (f)			
Specific diagnoses									
diagnosis 1									
diagnosis 2									
Diagnosis groupings									
grouping 1									
grouping 2									
Number of recipients experiencing a single diagnosis									
Number of recipients experiencing multiple different diagnoses									

N/A = Not Applicable

Table 5a: Frequency and rate of hospitalization and emergency events observed following vaccination with MenACWY-CRM

Event	Overall		Number of vaccines received prior to event							
			One		Two		Three		Four	
	Frequency n (%)	Rate (95% CI)*	Frequency n (%)	Rate (95% CI)*	Frequency n (%)	Rate (95% CI)*	Frequency n (%)	Rate (95% CI)*	Frequency n (%)	Rate (95% CI)*
Hospitalization only										
Emergency department only										
Emergency department and hospitalization										

*Events per 1000 person years

Table 5b: Frequency and rate of diagnoses observed following vaccination with MenACWY-CRM

Event	Overall		Number of vaccines received prior to event								Setting of initial presentation with the diagnosis*						First occurrence or recurrence			
			One		Two		Three		Four		Inpatient		Emergency		Both settings		First occurrence		Recurrence	
	Frequency n (%)	Rate (95% CI)*	Frequency n (%)	Rate (95% CI)*	Frequency n (%)	Rate (95% CI)*	Frequency n (%)	Rate (95% CI)*	Frequency n (%)	Rate (95% CI)*	Frequency n (%)	Rate (95% CI)*	Frequency n (%)	Rate (95% CI)*	Frequency n (%)	Rate (95% CI)*	Frequency n (%)	Rate (95% CI)*	Frequency n (%)	Rate (95% CI)*
Specific diagnoses																				
diagnosis 1																				
diagnosis 2																				
Diagnosis groupings																				
grouping 1																				
grouping 2																				
etc.																				

*Events per 1000 person years

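### Table 5b's recurrence rate has no at-risk denominator: it is a component of the overall rate and cannot be compared with the first-occurrence rate beside it

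*SAP*

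**What the plan says.** All references are to SAP v2.0 unless stated.

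- Section 5.2 gives one definition of a rate: "the number of all captured events divided by the total person-time following MenACWY-CRM doses administered during the study period".
- The same section sets out person-time by dose only. It runs from each vaccination for six months and stops earlier at the next dose, loss of membership, death or the close of data collection.
- It then splits the events: "captured medical events will be stratified by dose and by the status of the diagnosis as first occurrence or recurrence". No matching split of person-time is given.
- The split is conditional: "The analysis by diagnosis will be stratified by setting of diagnosis and recurrence when the number of events in each stratum is" at least 5. The footnote to the table list in section 8 repeats the threshold.
- Table shell 5b has a column block headed "First occurrence or recurrence". Each half has a frequency and a rate with 95% CI, footnoted "Events per 1000 person years". The shell has no person-years column.
- Section 5.1 defines a recurrence through its date: "the date used will be the date of the first diagnosis in the medical record following resolution of the prior episode". It also excludes a diagnosis whose code was already on record before the first dose.

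Protocol section 9.7.3 stratifies the rate by dose only. It asks for recurrence after repeated vaccination to be covered in the description of events. The rate split by recurrence status comes from the SAP.

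**The concern.** Earlier history is excluded and a recurrence needs a resolved episode. A counted recurrence can therefore come only from a child with a first episode inside the observation period, and only after that episode has ended. The remaining person-time cannot produce one, yet under the only stated definition it all enters the recurrence denominator. In the other direction, time after a first episode can no longer yield a first occurrence, but it stays in that denominator.

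The two rates are printed next to each other with intervals and in the same unit. A reader interested in whether an event comes back, which the protocol treats as worth describing, would naturally compare them. On this denominator their ratio is simply the ratio of the two counts. It says little about whether a child who has had the event is more or less likely to have it again.

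**Working it through.** **The plan's own figures.** The documents state no first-occurrence or recurrence rate. Their only rate figures are the expected intervals in SAP 3.2. These are exact Poisson limits, χ²(0.025; 2x)/2 and χ²(0.975; 2x+2)/2, with x = rate × N/100, divided by N person-years. For N = 100 and 10 per 100 person-years, x = 10 gives 4.8 to 18.4, as printed. Ten of the 12 intervals match; the other two differ by 0.1 in one limit. Their basis of one person-year per child is used below.

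**Inputs.** From SAP 3.2: T = 1 year of follow-up on average, and 60 to 100 children with high-risk conditions (80 used here). From SAP 5.2: at least 5 events per stratum for display. Assumed, not in the documents: constant hazards L1 (first) and L2 (recurrence), and an episode length d of 14 days.

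**Formulae.** With U = T − d:

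- First-occurrence rate on all person-time = (1 − exp(−L1·T))/T.
- Share of person-time at risk of a recurrence = [U − (1 − exp(−L1·U))/L1]/T.
- Recurrence rate on all person-time ≈ L2 × that share. This ignores the short time spent inside recurrent episodes, so simulated values are slightly lower.

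**One case by hand.** L1 = L2 = 0.3 per year and U = 1 − 14/365.25 = 0.962. First: 1 − exp(−0.3) = 0.259. Share: 0.962 − (1 − exp(−0.2885))/0.3 = 0.126. Recurrence: 0.3 × 0.126 = 0.038. Equal hazards of 300 per 1000 person-years thus print as 259 and 38, about 7-fold apart. In 80 children that is about 21 first occurrences but only 3 recurrences, below the display threshold.

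**With the display rule applied** (4,000 simulated cohorts of 80 children; rates per 1000 person-years):

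| True hazards, first / recurrence | Plan's rates, all cohorts | Columns shown in | First : recurrence when shown |
|---|---|---|---|
| 100 / 100 | 95 / 4.5 | almost never | – |
| 300 / 300 | 258 / 38 | 19% | about 3.9 |
| 600 / 600 | 451 / 136 | 97% | about 3.3 |
| 1000 / 1000 | 630 / 330 | 100% | about 1.9 |
| 300 / 1000 | 259 / 122 | about 93% | about 2.1, true ratio 0.3 |

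Dividing by person-time at risk recovers the true hazards in every row, within simulation error.

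**A case with fixed counts** (assumed: N = 100, T = 1, d = 0, 10 children with a first episode, 5 recurrences). It passes the display rule. On all person-time the rates are 10/100 = 100 and 5/100 = 50 per 1000. With L1 = −ln(0.9) = 0.105, time at risk of a first occurrence is 100 × 0.1/0.105 = 94.9 person-years, and time after onset is 100 − 94.9 = 5.1. The at-risk rates are about 105 and 983, so the order reverses.

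**The first-occurrence column.** Total person-time exceeds time up to first onset by a factor L1·T/(1 − exp(−L1·T)). This is 1.03 to 1.10 at 5 to 20 per 100 person-years, 1.27 at 50 and 1.58 at 100.

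**The case against.** The strongest reply is that nothing here is miscalculated. Recurrences over total person-time are a valid marginal rate: recurrent episodes per 1000 person-years of follow-up after vaccination. The first-occurrence and recurrence columns then add to the overall rate, and the setting columns split events in the same way. The study is descriptive, no comparison of the two columns is planned, and the counts stand beside the rates. All of this stands.

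A reader might go further and infer that the recurrence rate is many times too low, by 20-fold or more. The documents do not support that as a general statement. It is too low only if read as the risk of recurring, which the SAP does not say it is. The large factors belong to rare diagnoses, and the five-event rule will seldom let those be printed.

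The shared denominator is also inferred from the only definition given. The section 8 footnote may restrict person-time to recipients without prior history of the event. That still does not restrict it to children at risk of a recurrence.

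Finally, an at-risk recurrence rate is not free. Section 5.1 judges resolution in order to class a later mention as continuation or recurrence. It does not require a resolution date, and a child with no later mention may never be given one.

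What the reply leaves untouched is that the table labels neither column's denominator, and that the layout invites a comparison the figures cannot bear.

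**Conclusion.** The point holds as a matter of definition and labelling in SAP 5.2 and Table 5b. The recurrence rate as specified is a component of the overall rate, not a rate among children at risk, and it should not be compared with the first-occurrence rate.

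For strata likely to be displayed in a cohort of about 80, equal hazards would typically appear about 2- to 4-fold apart. The order can reverse when the recurrence hazard is high. Both statements rest on assumed constant hazards, 14-day episodes and one person-year per child; the documents give none of the hazards. The factor is larger for rarer diagnoses, whose strata will seldom be shown. The effect on the first-occurrence rate is small except for common diagnoses. The overall event rate is unaffected.

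**What to change.** In SAP 5.2 and Table shell 5b:

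1. Replace the recurrence rate with 'k of n children with a first episode had at least one recurrence', plus the number of recurrent episodes. Here n is the number of children with a first episode counted in Table 4b.
2. Compute the first-occurrence rate on person-time up to first onset. Section 5.1 already determines those dates.
3. Keep total person-time for the overall rate.
4. If a recurrence rate over total person-time is kept, label it as a component of the overall rate, and show person-years and the number of children at risk.

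An at-risk recurrence rate is optional. It would need resolution dates from chart review, or a stated rule for assigning them.

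The cost is a SAP wording change, a revised column block and a little extra programming. The downside is that the first-occurrence and recurrence figures would no longer sum to the overall rate, which a footnote should say.
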